12.1 Efficacy Parameters

12.1.1 VAS and NRS-11

Ear pain will be measured by VAS and NRS-11. Scores will be collected for each ear at Baseline and 10, 20, 30, and 60 minutes post dose.

The VAS consists of a 100 mm line anchored by 2 extremes of pain, with the left anchor representing "no pain" and the right anchor representing "worse pain." Study Participants mark the line where their pain is best represented between the 2 anchors. The VAS score is the distance from the left anchor to the Study Participant's mark.

Confidential Page 18 of 33

NRS-11 pain scores range from 0 to 10, with 0 representing "no pain" and 10 representing the "worst pain possible." NRS-11 \geq 5 reflects moderate to severe pain and is an inclusion criterion.

Listings will show observed values and absolute changes from baseline for each ear separately, for the sum over both ears, and for the maximum score across both ears. For both VAS and NRS-11, decreasing change scores from baseline indicate improvement and this will be footnoted in TFLs.

Endpoints

The following endpoints will be calculated for both VAS and NRS-11, unless otherwise indicated, using (a) the sum of scores over both ears, and (b) the maximum score across both ears:

- PID_{t_i} where i = 1 to 4 and t_1 , t_2 , t_3 , $t_4 = 10$, 20, 30, and 60 minutes post dose, respectively, and PID_{t_i} = score at time t_i score at baseline (ie, change from baseline).
- SPID_t I defined as

$$SPID_{t_{-}I} = \sum_{i=1}^{I} PID_{t_{-}i} (t_i - t_{i-1})$$

where I = 1 to 4, t_0 is baseline, and t_1 , t_2 , t_3 , t_4 are time points 10, 20, 30, 60 minutes post dose, respectively. For example, SPID₂ is the sum of changes from baseline at 10 and 20 minutes post baseline weighted by time (in minutes) since the previous measurement.

- Percent change from baseline (per inclusion criteria, baseline VAS and NRS-11 are unlikely to be 0).
- Presence of any pain, defined as score > 0 at 10, 20, 30, and 60 minutes post dose.
- Improvement categorized as "worsening" (positive change score), "no change" (0 change score), "improvement" (negative change score) at 10, 20, 30, and 60 minutes post dose.
- Time to pain relief defined as time point (10, 20, 30, 60 minutes post dose or no pain relief) at which relief was achieved, where "relief" is defined as score < 5 for NRS-11 and at least a 30 mm decrease from baseline for VAS. In the unlikely event that a Study Participant has a baseline VAS less than 30 mm, they will be excluded from the VAS analysis of time to pain relief.
- Response, defined as a 25%, 50%, and 75% reduction in score, at 10, 20, 30, and 60 minutes post dose.

Summaries and Analyses (see Section 13)

• PID_{t_i} will be analyzed using mixed model for repeated measures (MMRM). A summary table will include least-squares (LS) means and standard errors (SEs) for each treatment group and the estimate of treatment group difference with 80, 90, and 95% confidence intervals (CIs) for the difference and associated p-values. LS means and SEs will also be graphically displayed using a line chart. In addition, 80, 90, and 95% CIs and associated p-values for within-group mean changes from baseline will be included in the summary table.

Confidential Page 19 of 33

- SPID_{t_I} will be analyzed using mixed model for repeated measures (MMRM). A summary table will include least-squares (LS) means and standard errors (SEs) for each treatment group and the estimate of treatment group difference with 80, 90, and 95% confidence intervals (CIs) for the difference and associated p-values. LS means and SEs will also be graphically displayed using a line chart. In addition, 80, 90, and 95% CIs and associated p-values for within-group mean changes from baseline will be included in the summary table.
- Response will be analyzed using general estimating equations (GEE). A summary table will include LS means and SEs for each treatment group and the estimate of treatment group difference with 80, 90, and 95% CIs for the difference and associated p-values. Crude response rates will be graphically displayed using a bar chart.
- Percent change from baseline, presence of pain, improvement category, and time to pain relief will be summarized in tables but will not be subjected to statistical inference.

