The ear pain data will be listed. The analysis of ear pain will focus on change of pain from Baseline to assessment at 10 min (0-10 min), 20 min (0-20 min), 30 min (0-30 min), and 60 min (0-60 min). The change of ear pain from Baseline to assessment will be described as the change of the sum of pain of right and left ear, and in addition as the change in worst reported pain across both ears. Thereby, worst reported pain across both ears is defined as the worst pain of either the right or the left ear determined separately for baseline and the respective assessment. These measures will be summarised as described above for continuous variables and analysed for treatment effect as further delineated in the SAP. Hodges-Lehmann point estimate and 80% 2-sided CI for the median of treatment effect differences between active and placebo will be provided. If significance is found using 80% CIs, 90% and 95% CIs will also be tested. Furthermore, tables providing the incidence of pain score > 0 at each post-baseline timepoint will be displayed. Additionally, shift tables for incidence of change from Baseline at each post-baseline timepoint with three categories (1) 'no change', (2) 'worsening' (ie, higher score than baseline), and (3) 'improvement' (ie, lower score than baseline) will be produced to describe change from Baseline for right and left ear separately.

Changes from Baseline in the VAS and NRS-11 scores will be summarised by treatment using descriptive statistics for the following post-dose timepoints: 10, 20, 30, and 60 min. Statistical comparisons of ear pain, as measured by the VAS and the NRS-11, between the treatments at 60 min post dose will be performed using an ANOVA model. Time to ear pain relief in the

affected ears, recorded as change from moderate/severe pain to mild or no pain using the VAS and the NRS-11, will be summarised by treatment.

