4.2.2 Exploratory Endpoints

Exploratory endpoints are related to efficacy and success of blinding:

- Response on ear pain scores at 10, 20, 30, and 60 minutes post dose using the VAS and the NRS-11
- Pain Intensity Difference (PID) from Baseline of the VAS and the NRS-11 at 10, 20, 30, and 60 minutes post dose
- Sum Pain Intensity Difference (SPID) of the VAS and the NRS-11 over 60 minutes post dose
- Time to ear pain relief in affected ear(s), recorded as change from moderate/severe pain to mild or no pain using the VAS and the NRS-11
- PGIC measured at 10, 20, 30, and 60 minutes post dose
- CGI-I scale measured at 60 minutes post dose
- Presence of AOM symptoms
- Response on the Blinding Index at 60 minutes post dose
- Response on Device Experience Questionnaire Subject
- Response on Device Experience Questionnaire Study Staff Administering Treatment

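### Time to pain relief is not derived as the endpoint is defined: the single-ear NRS-11 cut is also put on the two-ear sum, and VAS relief is a 30 mm fall rather than a change to mild or no pain

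*SAP*

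**What the plan says.** The endpoint is described in the same terms in both documents. SAP 4.2.2 lists "Time to ear pain relief in affected ear(s), recorded as change from moderate/severe pain to mild or no pain", on the VAS and the NRS-11. Protocol 5.2.6.1 describes it the same way: "affected ears, recorded as change from moderate/severe pain to mild or no pain using the VAS and the NRS-11, will be summarised by treatment".

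SAP 12.1.1 gives the derivation. Relief is "score < 5 for NRS-11 and at least a 30 mm decrease from baseline for VAS", and the result recorded is the "time point (10, 20, 30, 60 minutes post dose or no pain relief) at which relief was achieved". The sentence that opens the endpoint list applies every item, on both scales, to "a) the sum of scores over both ears, and (b) the maximum score across both ears", except where an item says otherwise. The relief item makes no exception.

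The same section explains the NRS-11 cut: on a 0-10 score, a value of 5 or more "reflects moderate to severe pain and is an inclusion criterion". Protocol 3.3.1 uses the same 0-10 cut for entry. Neither document gives a VAS boundary between mild and moderate pain.

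There is also an exclusion. A subject with a "baseline VAS less than 30 mm, they will be excluded from the VAS analysis of time to pain relief". The SAP does not say whether that baseline is per ear, the sum or the maximum.

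On use, "time to pain relief will be summarized in tables but will not be subjected to statistical inference". The results go to Tables 14.2.1.5.1 (VAS) and 14.2.1.5.2 (NRS-11). SAP 15, which lists changes from the protocol, mentions neither the 30 mm rule nor the use of the sum for this endpoint.

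**The concern.** The definition describes a state that the affected ear reaches. The derivation departs from it in two ways.

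For NRS-11, a cut calibrated on one ear's 0-10 scale is applied unchanged to a 0-20 total, where it means an average below 2.5 per ear. A subject whose two ears are both mild can be recorded as relieved late, or never. This is not confined to bilateral disease. Both ears are scored whatever the laterality (SAP Appendix A), so a unilateral case with a low non-zero score in the other ear can also be misclassified.

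For VAS, the rule measures change and ignores the level reached, yet it is reported under the name of a state endpoint. The 30 mm is not rescaled for the 0-200 mm sum either.

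As a result, two tables with the same name report different events. On the sum, when both ears hurt, NRS-11 relief is pushed later and VAS relief tends to be pulled earlier. In a proof-of-concept study of pain reduction within 60 minutes, a reader could take that for a real difference between the scales in onset of relief.

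**Working it through.** The plan gives no figure that depends on this endpoint, so there is nothing to reproduce. The check is enumeration and arithmetic on the stated rules.

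**Inputs.** NRS-11 is 0-10 per ear (SAP 12.1.1, Protocol 3.3.1), so the sum is 0-20. Protocol 3.5.4 gives the range as 0 to 11, but that does not affect pairs below 5. VAS is 0-100 mm per ear (SAP 12.1.1), so the sum is 0-200 mm. Relief is a score below 5 (NRS-11) or a fall of at least 30 mm (VAS). About 24 subjects are planned, 12 per arm (Protocol 5.2.1).

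**NRS-11, sum against maximum**

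- Both ears below 5 means each scores 0-4: 5 × 5 = 25 pairs, all relieved on the maximum.
- Pairs with a sum of 5 or more: 1/4, 2/3, 2/4 and 3/4 in either order (8 pairs), plus 3/3 and 4/4 (2 pairs). That is 10 of 25, with sums from 5 to 8. The sum rule counts the other 15.
- None of the 10 contains a zero. With both ears above 0 the count is therefore 10 of 4 × 4 = 16. Among the five equal pairs, 2 fail.
- The number of the affected ear's five values (0-4) that fail the sum rule depends on the other ear:

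| Other ear's score | 0 | 1 | 2 | 3 | 4 |
|---|---|---|---|---|---|
| Values failing, of 5 | 0 | 1 | 2 | 3 | 4 |

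- Direction: the sum is never below the maximum, so no pair has a sum below 5 with an ear at 5 or more. Sum-based relief is never earlier than maximum-based relief.
- Required fall with equal ears: from 5/5 the maximum rule needs (5 − 4)/5 = 20% and the sum rule (10 − 4)/10 = 60%. From 10/10 they need (10 − 4)/10 = 60% and (20 − 4)/20 = 80%.

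These are counts of possible scores, not expected frequencies.

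**VAS, change against state**

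- 100 − 30 = 70 mm, so a subject can be relieved while still at 70 mm. A move from 50 to 21 mm is a 29 mm fall and is not relief.
- Illustration only, with an assumed mild boundary *c*: relief can be recorded at or above *c* when baseline is at least *c* + 30. A move below *c* can be missed when baseline is under *c* + 30. For *c* = 30, 40 or 50 mm, that turning point is 60, 70 or 80 mm.

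**VAS, sum against maximum**

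- With equal falls, 30 mm on the sum is 30/2 = 15 mm per ear. From 60/60 to 45/45 the sum falls 120 − 90 = 30 mm (relief), a 15/60 = 25% reduction. The maximum falls only 15 mm (no relief).
- Direction: let the baselines be B1 ≥ B2 and the later scores S1 ≤ B1 and S2 ≤ B2. The maximum falls by B1 − max(S1, S2) ≤ B1 − S1 ≤ (B1 − S1) + (B2 − S2), which is the fall in the sum. So if neither ear is above its baseline, sum-based relief is never later. A 5 mm grid has 21 values per ear and 21 × 22/2 = 231 non-worsening moves per ear. All 231² = 53,361 combinations agree.

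**Baseline exclusion.** At 20/20 mm the sum is 40 mm (included) and the maximum is 20 mm (excluded).

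**The case against.** The strongest case is that little hangs on this. The endpoint is one of many exploratory ones in a study of about 24 subjects and carries no inference. The NRS-11 endpoint is already delivered by the maximum version. The sum version is a stricter extra that never credits false relief, and per-ear, sum and maximum scores are all listed. Those points are right, and they limit the effect to two descriptive tables. They do not make the sum rule fit its definition. Protocol 5.2.6.1 does call for sum and worst-ear scores, but for change in ear pain; it states time to relief separately, for the affected ears.

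A second argument is that the protocol leaves detail to the SAP and lets the SAP prevail, and that no protocol VAS threshold was replaced. That answers a conflict between protocol and SAP. It does not answer one between SAP 4.2.2 and SAP 12.1.1.

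Third, the claim about VAS direction is conditional. If the other ear worsens, it can reverse: from 80/0 to 50/5 mm the maximum falls 30 mm but the sum only 80 − 55 = 25 mm. This stands, so the direction is claimed only when neither ear is above baseline.

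Fourth, the maximum over both ears does not strictly isolate the affected ear(s). That also stands, and the SAP should name one basis. It does not rescue the sum.

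Finally, renaming the VAS measure does not restore a state-based VAS endpoint. That is true. The documents supply no boundary from which to build one.

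**Conclusion.** The concern holds. Followed literally, SAP 12.1.1 classifies subjects in a way that conflicts with SAP 4.2.2 and Protocol 5.2.6.1, and SAP 15 does not record it.

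The NRS-11 fault is confined to the sum version; the maximum version fits the cut. The VAS fault affects both versions: the label is wrong on each, and on the sum the threshold is effectively halved when both ears fall equally.

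The effect is limited to Tables 14.2.1.5.1 and 14.2.1.5.2. No test, confidence interval, sample size or safety conclusion changes. The number of subjects affected cannot be estimated, because the documents give neither the share of bilateral cases nor the scores expected in the other ear. With 12 per arm, each reclassified subject moves an arm's percentage by 1/12, about 8 points.

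The NRS-11 and sum-against-maximum results need no distributional assumption. The only assumed figures are the illustrative VAS boundaries of 30 to 50 mm, and the conclusion does not rest on them. The plan should be corrected, but nothing inferential depends on it.

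**What to change.** 1. **NRS-11.** State that time to relief is derived on the maximum score, or on the affected-ear score if that is preferred. Name one and drop the sum version.
2. **VAS.** Rename the measure as time to a reduction of at least 30 mm. Derive it and its 30 mm baseline exclusion on the maximum score, and do not describe it as a change to mild or no pain.
3. **Consistency.** Amend SAP 4.2.2 and the title of Table 14.2.1.5.1 to match, and record both changes in SAP 15 before unblinding.

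A state-based VAS cut is optional. It would have to be justified from outside these documents.

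The cost is SAP wording, two derivations and one table title, with no new data. The sum-based time-to-relief results are lost but can be rebuilt from the listings. The VAS is left without a state-based relief endpoint. A subject with both ears below 30 mm but a sum of 30 mm or more would leave the VAS analysis; the SAP itself regards a baseline below 30 mm as unlikely.

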12.1.2 PGIC and CGI-I

PGIC scores will be collected at 10, 20, 30, and 60 minutes post dose. Study Participants will be asked "How have your symptoms been since you received the study treatment?" Scores range from 1 to 7 with 1 = very much improved, 2 = much improved, 3 = minimally improved, 4 = no change, 5 = minimally worse, 6 = much worse, and 7 = very much worse.

CGI-I score will be collected at 60 minutes post dose. Physician investigators will be asked "How has the subject's symptoms been since they received the study treatment?" The score range and meaning of each score are the same as for PGIC described above.

Listings will show observed values. Lower scores indicate better symptom status and this will be footnoted in TFLs.

Endpoints

The following endpoints will be calculated for both PGIC and CGI-I at each time point collected:

- Observed value.
- Response, defined as much improved or very much improved.

Summaries and Analyses (see Section 13)

- PGIC observed value will be analyzed using MMRM with baseline NRS-11 as a covariate. A summary table will include LS means and SEs for each treatment group and the estimate of treatment group difference with 80, 90, and 95% CIs for the difference and associated p-values. LS means and SEs will also be graphically displayed using a line chart. Frequency distributions of observed responses will also be summarized.
- CGI-I observed valued will be analyzed using GLM with baseline NRS-11 as a covariate. A summary table will include LS means and SEs for each treatment group and the estimate of treatment group difference with 80, 90, and 95% CIs for the difference and associated p-values. Frequency distributions of observed responses will also be summarized.
- Response will be analyzed using GEE with baseline NRS-11 as a covariate (if convergence can be achieved). A summary table will include LS means and SEs for each treatment group

Confidential Page 20 of 33

and the estimate of treatment group difference with 80, 90, and 95% CIs for the difference and associated p-values.

12.1.3 AOM Symptoms

AOM symptoms are tinnitus, dizziness, vertigo, and feeling of fullness or muffled hearing in the ear. Presence/absence of each AOM symptom will be collected at Baseline and 60 minutes post dose.

Endpoints

The endpoint for each symptom will be presence of the symptom.

Summaries and Analyses

• Presence of each symptom will be summarized but not subjected to statistical inference.

12.2 Blinding Index

Success of blinding will be measured by the Bang Blinding Index.⁸ Success of blinding will be measured for both physician investigators and Study Participants at the completion of Day 1 assessments but prior to administering the Device Experience Questionnaire. Study Participants will be asked to guess which treatment they received and will be asked for a "best guess" if they respond "I don't know." Similarly, physician investigators will be asked to guess which treatment the Study Participant received. Reason(s) for responses given will be entered into the eCRF as free text.

The Blinding Index will be listed and summarized for Study Participants in the Safety Population, separately for Study Participants and physician investigators.

Endpoints

The endpoint will be response to the question "Which treatment do you believe you received?" or, for physician investigators, "Which treatment do you believe the subject received?" The possible responses are:

- 1 = strongly believes real medication was received
- 2 = somewhat believes real medication was received
- 3 = somewhat believes placebo was received
- 4 = strongly believes placebo was received
- 5 = doesn't know

If the response is "don't know," the respondent is asked to provide their best guess as to which treatment, real medication or placebo, was received.

Summaries and Analyses

The Bang Blinding Index for the ith treatment group, i = 1 for OP0201 and 2 for placebo, will be calculated as

Confidential Page 21 of 33

$$P_{1|i} + w_{2|i}(P_{2|i}) + w_{31|i}(P_{31|i}) - P_{3|i} - w_{4|i}(P_{4|i}) - w_{32|i}(P_{32|i})$$

where:

 $P_{j|i}$ = probability of response j, j = 1 to 4, given treatment i was assigned, estimated by $n_{ij}/n_{.j}$ where n_{ij} is the number of Study Participants in the ith treatment group who gave response j and $n_{.j}$ is the total number of Study Participants who gave response j.

 $P3_{k|i}$ = probability of response k to the "best guess" question, k = 1 to 2 with 1 = real medication and 2 = placebo, given treatment i was received, estimated by $n_{ik}/n_{.k}$ where n_{ik} is the number of Study Participants in the ith treatment group who gave response k and $n_{.k}$ is the total number of Study Participants who gave response k.

 $w_{i|i}$ = weights for $P_{i|i}$, suggested by Bang to be set to 0.5.

 $w3_{k|i}$ = weights for $P3_{k|i}$ suggested by Bang to be set to 0.25.

12.3 Device Experience Questionnaire

Experience with the device during the study will be measured by the Device Experience Questionnaire and will be collected from both physician investigators and Study Participants at the completion of all Day 1 assessments. Data collection will be external to the eCRF. Any study staff who administered treatment to Study Participants will also complete the Device Experience Questionnaire one time only (not for each Study Participant treated). These data will be summarized but not subjected to statistical inference.

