1.4 Study Endpoint Rationale

The primary endpoint in this study is to evaluate the safety of a single intranasal dose of OP0201 20 mg in adults with AOM. Spontaneously reported AEs, vital signs measurements, and ear, nose, and throat (ENT) examination findings will be used to assess the safety of OP0201. The ENT examination findings will be used to evaluate any AEs of the ear, nose, and oropharynx that occurred during treatment. Vital signs measurements will be used to evaluate whether any clinically significant changes in blood pressure, pulse, respiratory rate, and oral temperature occurred post dose.

All efficacy assessments will be exploratory endpoints and were selected to evaluate reduction of ear pain and symptoms associated with AOM.

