3 INVESTIGATIONAL PLAN

3.1 Overall Study Design and Plan

This will be a single-dose, double-blind, placebo-controlled, randomised, parallel-group, proof-of-concept study to evaluate the safety and immediate (within 60 min) reduction of ear pain caused by AOM in adults following a single dose of intranasal OP0201 20 mg or placebo.

All study-related procedures, including screening, will be performed on Day 1. Following Screening, but before any treatment-related procedures, eligible subjects will be randomly assigned to 1 of the following groups:

- Single intranasal dose of OP0201 20 mg (4 sprays per nostril for a total of 8 sprays)
- Single intranasal dose of placebo (4 sprays per nostril for a total of 8 sprays)

Ear pain will be assessed in the left and the right ear separately, at predose and at 10, 20, 30, and 60 min post dose using the VAS and the NRS-11. Global impression of change in symptoms will be rated by the subject at 10, 20, 30, and 60 min post dose using the PGIC. The physician investigator will rate global impression of change at 60 min post dose using the CGI-I. AOM symptoms (tinnitus, dizziness, vertigo, and feeling of fullness or muffled hearing in the ear) will also be evaluated at predose and at 60 min post dose.

Safety evaluations include vital signs measurements, ENT examination using otoscopy, appearance of the TM, and AEs. Vital signs (oral temperature, respiratory rate, pulse, and blood

pressure) will be measured (after 3 min of rest in the supine position) predose and at 60 min post dose. An ENT examination (otoscopy of the ear, nose, and oropharynx) will be performed by the physician investigator (physician qualified to perform an otoscopic exam of the ears, nose, and oropharynx) at predose and at 60 min post dose. All spontaneously reported AEs will be recorded. The appearance of the TM (contour, color, fluid, and translucency) will also be evaluated using otoscopy by the physician investigator at predose and at 60 min post dose. The appearance of the TM will be evaluated in both ears separately, regardless if AOM is bilateral or unilateral.

After the subject has completed all assessments on Day 1, the BI will be administered separately to the subject and physician investigator prior to the subject leaving the study centre. The Device Experience Questionnaire will be administered to the subject following the BI before the subject leaves the centre.

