3.5.5 Safety Assessments

Ear, Nose, and Throat Examination: Examination of the ear, nose, and oropharynx will be performed using otoscopy at Screening and at 60 min post dose.

Otoscopy: Otoscopy assessments will be performed by the physician investigator to assess the appearance of the TM in the left and right ear. Measurements will be taken at Baseline and at 60 min post dose. The TM will be rated for the following variables:

- Contour: normal, retracted, full, bulging, or perforated
- Color: normal, partly red, or completely red
- Fluid behind the TM: no/yes; if yes-yellow, translucent, red, blue, or black
- Translucency: translucent, semi-opaque, or opaque

Details of how each variable is to be assessed and categorised are provided in Appendix 8.2.

Vital Signs: Vital signs will be measured at Baseline and at 60 min post dose or Early Termination. Vital signs will include oral temperature (C), respiratory rate (breaths per minute), pulse (beats per minute [bpm]), and systolic and diastolic blood pressure (BP) recorded after at least 3 min of rest in the supine position. Body weight (kg) will also be collected with the vital signs measurements at Baseline only. Repeat measurements may be obtained in the event the initial measurements taken at Baseline are out of range.

Adverse Events: All AEs occurring after the administration of study treatment until the follow-up safety call or early termination will be recorded.

See Section 4, for additional information.

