4.1 Definitions and Criteria

4.1.1 Adverse Events

Per ICH E2A²⁹: An AE is any untoward medical occurrence in a patient or clinical investigation subject administered a pharmaceutical product and which does not necessarily have to have a causal relationship with this treatment. An AE can therefore be any unfavorable and unintended sign (including an abnormal laboratory finding, for example), symptom, or disease temporally associated with the use of a medicinal product, whether or not considered related to the medicinal product.

Medical interventions such as surgeries, diagnostic procedures, and therapeutic procedures are not AEs but the action taken to treat the medical condition. They should be recorded as treatment of the AEs.

Any AE that has an onset on or after the dose of study drug, or any pre-existing condition that has worsened on or after the first dose of study drug will be considered a treatment-emergent adverse event (TEAE).

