5.3 Analysis of Other Assessments

The BI will be administered following completion of all other assessments, except the Device Experience Questionnaire, on Day 1. Responses on the BI will be summarised separately for the subject and physician investigator.

The Device Experience Questionnaires will be analyzed at a later date.

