8.3 Device Experience Questionnaire-Study Staff Administering Treatment

For Clinical Staff

Thank you for completing the study activity. Please rate your agreement to the following statements and circle your response.

1. My first reaction to the study inhaler was positive.

	Strongly Disagree	Disagree	Neutral	Agree	Strongly Agree		
2.	The study inhaler Instructions for Use were clear and easy to follow.						
	Strongly Disagree	Disagree	Neutral	Agree	Strongly Agree		
3.	If I was not instructed	d, I feel confident tha	t I could have used th	e product witho	ut instruction.		
	Strongly Disagree	Disagree	Neutral	Agree	Strongly Agree		
4.	The study inhaler is e	easy to use.					
	Strongly Disagree	Disagree	Neutral	Agree	Strongly Agree		
5.	It was easy to place t	he study inhaler in th	e nostril.				
	Strongly Disagree	Disagree	Neutral	Agree	Strongly Agree		
6.	It was easy to press o	lown on the study inh	naler.				
	Strongly Disagree	Disagree	Neutral	Agree	Strongly Agree		
7.	Other comments.						
		ç					

Thank you, please hand the questionnaire back to the Principal Investigator.

Site No. Date

For Trial Subjects

Thank you for completing the study activity. Please rate your agreement to the following statements and circle your response.

1. My first reaction to the study inhaler was positive.

	Strongly Disagree	Disagree	Neutral	Agree	Strongly Agree						
Co	mments:				R						
2.	The study inhaler was comfortable in my nostril.										
	Strongly Disagree	Disagree	Neutral	Agree	Strongly Agree						
Co	mments:										
3.	3. The spray had a pleasant taste or aroma.										
	Strongly Disagree	Disagree	Neutral	Agree	Strongly Agree						
Comments:											
4.	4. There was no discomfort or irritation from the spray inside of the nose.										
	Strongly Disagree	Disagree	Neutral	Agree	Strongly Agree						
Co	mments:										
5.	Other comments	5.									
	9										

Thank you, please hand the questionnaire back to the Principal Investigator.

Subject No.	Site No.	Date

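### AE capture relies on spontaneous reports, and no step carries two sets of answers already collected (nasal irritation, new AOM symptoms) into the safety outputs

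*SAP*

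**What the plan says.** **AE capture.** Protocol 3.1 states "All spontaneously reported AEs will be recorded", and the synopsis says the same. Protocol 1.4 names the sources for the primary endpoint: "Spontaneously reported AEs, vital signs measurements, and ear, nose, and throat (ENT) examination findings will be used to assess the safety of OP0201". Neither document describes a solicited local-tolerability question within AE collection. The recording rule in Protocol 3.5.5 is broader: "All AEs occurring after the administration of study treatment until the follow-up safety call or early termination will be recorded".

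**Nasal irritation.** Item 4 of the subject form (Protocol 8.3) asks for agreement with "There was no discomfort or irritation from the spray inside of the nose". Protocol 3.5.2.2 lists the 60-minute AE check, then the Blinding Index, then this questionnaire; Protocol 3.5.6 confirms that the questionnaire comes after the Blinding Index. On data handling, SAP 12.3 says "Data collection will be external to the eCRF" and adds that the data will be summarised. Protocol 5.3 says "The Device Experience Questionnaires will be analyzed at a later date". SAP 4.2.2 lists the questionnaire among the exploratory endpoints. SAP 8.2 points to Appendix B for the outputs to be produced, and no questionnaire table or listing appears there.

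**AOM symptoms.** The investigator records tinnitus, dizziness, vertigo and fullness or muffled hearing as present or absent, predose and at 60 minutes (Protocol 3.5.4). SAP 12.1.3 says "Presence of each symptom will be summarized but not subjected to statistical inference". The output is Table 14.2.3, placed with the exploratory endpoints. ENT and otoscopy findings, by contrast, get shift tables (SAP 11.2 and 11.3).

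**The concern.** The primary objective is safety, and Protocol 1.1.2 says OP0201 has not yet been evaluated in clinical studies in humans. Both arms receive eight propellant sprays into the nose. The one question about nasal irritation that every subject must answer sits in a device questionnaire. It comes after the scheduled Day 1 AE check and has no data path into the safety tables. A subject who disagrees with item 4 has told the study about a possible local reaction, yet no written step asks anyone to consider whether it is an AE.

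The AOM symptom data raise a similar issue. A symptom absent predose and present at 60 minutes may be a treatment-emergent event. A table of presence at each time point shows only the net change, and no step requires new onsets to be checked against the AE form.

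With 12 subjects per arm, one unrecorded case changes an arm's rate from 1/12 (8.3%) to 0/12. The study could then report a cleaner tolerability profile than its own data support.

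**Working it through.** The plan gives no figure to reproduce here. Protocol 5.2.1 gives about 24 subjects, 12 per arm, without a power basis. The check has three parts.

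**1. Where each answer goes**

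| Information | Where it is asked | Route to safety outputs |
|---|---|---|
| Visible nose, ear or throat reaction | 60-minute ENT examination | Tables 14.3.7.1 and 14.3.7.2 |
| Volunteered symptom | AE recording, post-dose to Day 7 | TEAE tables, or the non-TEAE table if onset is after Day 2 |
| Subjective nasal irritation, asked of all | Questionnaire item 4 | None written; no output in Appendix B |
| New tinnitus, dizziness, vertigo or fullness | AOM symptom check | Table 14.2.3 (exploratory) and Listing 16.2.6.4; no written check against the AE form |

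A new symptom at 60 minutes falls within the protocol's timing for a TEAE, "Any AE that has an onset on or after the dose of study drug", and within the SAP's Day 1 to Day 2 window (SAP 11.1).

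**2. What incomplete capture does to nasal discomfort**

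Inputs: incidence p = 0.048 (Protocol 1.5, propellant placebo, n = 578) and n = 12 per arm. The share volunteered without prompting, c, is an assumption; the documents give none.

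P(at least one recorded case in an arm) = 1 − (1 − p·c)^12

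- c = 1: 1 − 0.952^12 = 44.6%
- c = 0.75: 1 − 0.964^12 = 35.6%
- c = 0.50: 1 − 0.976^12 = 25.3%
- c = 0.25: 1 − 0.988^12 = 13.5%

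If the true single-dose incidence were 10% (assumed), the c = 1 and c = 0.50 values would be 71.8% and 46.0%; at 20%, 93.1% and 71.8%.

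Zero recorded cases in 12 gives a one-sided 95% upper bound of 1 − 0.05^(1/12) = 22.1%. That bound describes true incidence only if capture is complete.

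**3. What a presence-only table hides**

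In one arm of 12, let a = present at both times, b = resolved and c′ = newly present. The table shows a + b before and a + c′ after. Suppose both are 6. Then b = c′, and the number of new onsets can be anything from 0 to 6. The table cannot distinguish six unchanged subjects from six resolutions offset by six new onsets.

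**The case against.** The strongest reply is that the plan already requires these events to be recorded.

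- Protocol 3.5.5, 4 and 4.2.1 call for all AEs to be recorded, and 3.4.7.1 makes an illness detected or worsened during the study an AE. The window stays open to the Day 7 call, so a form completed after the 60-minute check is not too late.
- The subject hands the questionnaire back to the Principal Investigator (Protocol 8.3), so an adverse answer can reach the person responsible for AE reporting.
- The investigator personally records the AOM symptoms, and AE recording comes next in the 60-minute list. Listing 16.2.6.4 lets a reader find each new onset among about 24 subjects.
- The ENT examination is an objective local check within the primary endpoint.
- Protocol 5.2 lets the SAP override the protocol on analyses, so the deferral in 5.3 gives way to the summary promised in SAP 12.3.

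All of this stands, and it rules out four stronger readings that a reader might draw:

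1. *AE capture is limited to spontaneous reports.* The sections above are wider than that. The plan relies on spontaneous reports without excluding others.
2. *Dizziness, vertigo and tinnitus are expected drug reactions.* The documents present them only as AOM symptoms, and Protocol 1.5 says the expected risks are unknown.
3. *The chance of at least one nasal-discomfort case among 24 subjects, 1 − 0.952^24 = 69%, measures the defect.* It is the chance that a case occurs, not that one is missed.
4. *Table 14.2.3 cannot show a drug effect.* Comparing 60-minute prevalence by arm remains a valid randomised comparison. Subjects without the symptom at baseline can dilute an effect but do not abolish it.

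Three gaps remain. A general duty to record AEs is not a step that links item 4 or a new symptom to the AE form. The ENT examination does not measure subjective discomfort. The promised questionnaire summary has no planned output.

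**Conclusion.** The point holds in a narrow form. Followed as written, the plan leaves tolerability answers it already collects out of its primary safety outputs, and its symptom table lets new onsets and resolutions offset each other. What may be missed is mainly subjective nasal discomfort or irritation; visible reactions are covered. For AOM symptoms the weakness lies in presentation and reconciliation, because the subject-level data are listed.

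The size is illustrative. At 4.8%, if half the cases are volunteered, the chance that an arm shows any case falls from 44.6% to 25.3%. This rests on an assumed capture share and on a rate taken from 2-6 week rhinitis trials. A single dose in AOM may differ in either direction. Disagreement with item 4 is a device rating that may indicate a reaction; whether it is an AE needs the investigator's assessment.

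No planned test or sample size changes. The case for acting is that the data already exist and the correction is cheap. The mismatch between SAP 12.3 and Appendix B needs correcting in any event.

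**What to change.** 1. **Protocol 3.5.6 and 4.2.1.** When the subject returns the questionnaire, and before the subject leaves, the investigator checks item 4 and its comments. A negative answer (disagree or strongly disagree) or an adverse comment prompts an assessment of whether an AE occurred and should be entered in the eCRF.
2. **SAP 12.3 and Appendix B.** Add a by-arm table and a listing of item 4, labelled as local tolerability and placed with the safety outputs. Align Protocol 5.3 with SAP 12.3 on when the questionnaire is analysed.
3. **SAP 12.1.3 and Table 14.2.3.** Lay out each AOM symptom by baseline status: resolved among those who had it, newly present among those who did not. Check each new onset against the AE listing before database lock.

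The cost is one short review per subject, one new table and listing, and one table relaid. Item 4 is held outside the eCRF, so its data must be transferred for analysis. The downside is a few more mild AEs, expected in both arms because both receive the propellant and the same check. No new assessment of subjects is needed.
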